12.8 Interim analyses

Not applicable.

12.9 Sample size calculation

12.9.1 Primary endpoint

A total of 40 subjects will be enrolled in this study i.e., 20 subjects per treatment arm. Based on the feedback from dermatologists with experience in prescribing biologic treatments for psoriasis (there is no historical data in the literature), the response rates to treatment are assumed to be 35% for guselkumab and 75% for secukinumab.

Table 12-1 presents the 95% exact confidence interval for different P1 (proportion of responders in the secukinumab arm) and P2 (proportion of responders in the guselkumab arm) and their corresponding difference P1-P2, together with the estimated power of a 1-sided Fisher's exact test at the target 1-sided Type I error rate of 5%.

For the favorable P1 = 0.75 and P2 = 0.35 values, the Fisher's exact test at the target Type I error of 5% will correctly reject H0: P1-P2 ≤ 0 with the power of 0.72%.

Table 12-1 Exact 95% confidence intervals for P1 and P2, the corresponding difference P1-P2, and the estimated power of the Fisher's exact test for different P1 and P2 values

Proportion (number) of responders in the secukinumab arm at Week 16: P1	Proportion (number) of responders in the guselkumab arm at Week 16: P2	95% exact confidence interval for P1	95% exact confidence interval for P2	95% exact confidence interval for P1-P2	Power of a 1-sided Fisher's exact test: H1: P1-P2 > 0
0.60 (12)	0.20 (4)	(0.36, 0.80)	(0.05, 0.43)	(0.10, 0.66)	75%
0.65 (13)	0.25 (5)	(0.40, 0.84)	(0.08, 0.49)	(0.06, 0.66)	72%
0.70 (14)	0.30 (6)	(0.45, 0.88)	(0.11, 0.54)	(0.09, 0.64)	71%
0.75 (15)	0.30 (6)	(0.50, 0.91)	(0.11, 0.54)	(0.13, 0.70)	82%
0.75 (15)	0.35 (7)	(0.50, 0.91)	(0.15, 0.59)	(0.06, 0.66)	72%
0.75 (15)	0.40 (8)	(0.50, 0.91)	(0.19, 0.63)	(0.01, 0.62)	61%
0.80 (16)	0.40 (8)	(0.56, 0.94)	(0.19, 0.63)	(0.10, 0.66)	75%

13 Ethical considerations and administrative procedures

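### Section 12.9.1 gives the planning power as 0.72%; the stated test has 72.4% power, and Table 12-1 prints 72% for the same scenario

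*Protocol*

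**What the plan says.** Everything relevant is in Protocol Section 12.9.1.

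- **Size:** "A total of 40 subjects will be enrolled in this study i.e., 20 subjects per treatment arm".
- **Planning rates:** "the response rates to treatment are assumed to be 35% for guselkumab and 75% for secukinumab". The protocol attributes these to feedback from dermatologists, because no historical data were available.
- **Test:** Table 12-1 is introduced as listing exact confidence intervals "together with the estimated power of a 1-sided Fisher's exact test at the target 1-sided Type I error rate of 5" per cent.
- **Power in the text:** for P1 = 0.75 and P2 = 0.35 the test is said to reject the null hypothesis "with the power of 0.72", followed directly by a percent sign.
- **Power in the table:** the row for the same two rates reads "0.75 (15) 0.35 (7) (0.50, 0.91) (0.15, 0.59) (0.06, 0.66) 72", again followed by a percent sign. Its last column is the power.

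The protocol summary and Section 12.4.2 describe the same test but give no power.

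**The concern.** The sentence and the table row describe one quantity: the same test, the same arm sizes and the same pair of response rates. One gives 0.72% and the other 72%, so they cannot both be right.

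The power at the planning rates is the figure on which the choice of 40 subjects is judged. Outside the table, this sentence is the only place that states it. Taken at face value, it says the trial would almost never detect the effect it was designed to detect. It also puts the power below the 5% Type I error rate given in the same sentence. The check therefore has two parts: which figure is right, and whether the table can be trusted.

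**Working it through.** **Inputs (all from Section 12.9.1).** n = 20 per arm; P1 = 0.75 (secukinumab); P2 = 0.35 (guselkumab); 1-sided Fisher's exact test; reject when p ≤ 0.05.

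**Formulas.** Let a and b be the responder counts on secukinumab and guselkumab. The 1-sided Fisher p-value is

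p(a, b) = Σ C(20, k) · C(20, a + b − k) / C(40, a + b), summed over k = a, …, min(20, a + b).

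The power is the probability of all outcomes that reject:

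Power = Σ over b of Pr[Bin(20, 0.35) = b] × Pr[Bin(20, 0.75) ≥ a*(b)],

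where a*(b) is the smallest a with p(a, b) ≤ 0.05.

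**Example of the cut-off.** With b = 7, p(13, 7) = 0.0564 and p(14, 7) = 0.0281, so a*(7) = 14.

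**Sum over b.**

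| b | a*(b) | Pr(B = b) | Pr(A ≥ a*) | Product |
|---|---|---|---|---|
| 0 | 5 | 0.0002 | 1.0000 | 0.0002 |
| 1 | 6 | 0.0020 | 1.0000 | 0.0020 |
| 2 | 8 | 0.0100 | 0.9998 | 0.0100 |
| 3 | 9 | 0.0323 | 0.9991 | 0.0322 |
| 4 | 10 | 0.0738 | 0.9961 | 0.0735 |
| 5 | 12 | 0.1272 | 0.9591 | 0.1220 |
| 6 | 13 | 0.1712 | 0.8982 | 0.1538 |
| 7 | 14 | 0.1844 | 0.7858 | 0.1449 |
| 8 | 15 | 0.1614 | 0.6172 | 0.0996 |
| 9 | 16 | 0.1158 | 0.4148 | 0.0481 |
| 10 | 16 | 0.0686 | 0.4148 | 0.0285 |
| 11 | 17 | 0.0336 | 0.2252 | 0.0076 |
| 12 | 18 | 0.0136 | 0.0913 | 0.0012 |
| 13 | 19 | 0.0045 | 0.0243 | 0.0001 |

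For b = 14 and 15 the products are below 0.0001. For b ≥ 16 no outcome rejects. At full precision the sum is **0.7236**, so the power is 72.4% and the Type II error is 1 − 0.7236 = 0.2764, or 27.6%. The b = 7 row alone contributes 14.5 percentage points, about twenty times the 0.72% in the text.

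**The table's power column.** The same enumeration was run for every row:

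| P1 | P2 | Printed | Computed |
|---|---|---|---|
| 0.60 | 0.20 | 75% | 0.7535 |
| 0.65 | 0.25 | 72% | 0.7236 |
| 0.70 | 0.30 | 71% | 0.7132 |
| 0.75 | 0.30 | 82% | 0.8233 |
| 0.75 | 0.35 | 72% | 0.7236 |
| 0.75 | 0.40 | 61% | 0.6100 |
| 0.80 | 0.40 | 75% | 0.7535 |

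All seven agree.

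**Could another method give 0.72%?** At 0.75 versus 0.35 with 20 per arm:

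- 2-sided Fisher at 0.05: 61.4%
- 1-sided Fisher at 0.025: 61.4%
- normal approximation, 1-sided: 83.7%
- normal approximation, 2-sided: 73.8%

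None is near 0.72%.

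**Is the literal figure possible?** With equal true rates in both arms, taken in steps of 0.05 from 0.05 to 0.95, the test's largest rejection probability is 0.0265, at a common rate of 0.30. A power of 0.0072 would mean the test rejects less often at a 40-point advantage for secukinumab than it does at that null point.

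**The case against.** The best answer is that this is a slip of units and not a miscalculation. The digits 0.72 are the correct power as a proportion, and only the percent sign is wrong. The section moves between the two notations, writing P1 = 0.75 in one place and 35% in another, so the cause is easy to see. The correct value stands in the table directly below, and no reader would believe that 40 subjects were planned for a power below the significance level. On that view the slip misleads nobody and changes nothing.

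Most of this stands. The calculation behind the sentence was evidently right, a reader who consults the table recovers the intended figure, and no analysis or conduct depends on the sentence. What does not follow is that it can be left alone. The printed number is wrong, nothing else in the protocol corrects it, and it states the power in the section that justifies the sample size.

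**Conclusion.** The concern holds. The text states 0.72%; the test it describes has 72.4% power, and Table 12-1 correctly prints 72%. The error is a factor of 100 and editorial in nature. The sample size of 40, the choice of test, the power column and the confidence intervals are not called into question.

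The result rests only on inputs given in Section 12.9.1: 20 per arm, rates of 0.75 and 0.35, and a 1-sided Fisher's exact test that rejects at p ≤ 0.05. It needs no outside assumption. That the cause is a stray percent sign is an inference, but the correction does not depend on it.

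**What to change.** In Section 12.9.1, change the power in the sentence on P1 = 0.75 and P2 = 0.35 to 72%, or to 0.72 with the percent sign removed. Using 72% matches the notation in the last column of Table 12-1.

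The table, the sample size and the analysis need no change. The cost is one text correction, which can go into the next protocol amendment.

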13.1 Regulatory and ethical compliance

This clinical study was designed and shall be implemented, executed and reported in accordance with the ICH Harmonized Tripartite Guidelines for Good Clinical Practice, with applicable local regulations (including European Directive 2001/20/EC, US CFR 21), and with the ethical principles laid down in the Declaration of Helsinki.

13.2 Responsibilities of the Investigator and IRB/IEC

Before initiating a study, the Investigator/institution must obtain approval/favorable opinion from the IRB/IEC for the study protocol, written informed consent form, consent form updates, subject recruitment procedures (e.g., advertisements) and any other written information to be provided to subjects. Prior to study start, the Investigator is required to sign a protocol signature page confirming his/her agreement to conduct the study in accordance with these documents and all of the instructions and procedures found in this protocol and to give access to all relevant data and records to Novartis monitors, auditors, Novartis Quality Assurance representatives, designated agents of Novartis, IRBs/IECs, and regulatory authorities as required. If an inspection of the clinical site is requested by a regulatory authority, the Investigator must inform Novartis immediately that this request has been made.

13.3 Publication of study protocol and results

The protocol will be registered in a publicly accessible database such as clinicalstudies.gov and as required in EudraCT. In addition, after study completion (e.g., defined as last patient last visit) and finalization of the study report the results of this study will be submitted for publication and posted in a publicly accessible database of clinical study results, such as the Novartis clinical study results website and all required Health Authority websites (e.g., Clinicalstudies.gov, EudraCT etc.).

For details on the Novartis publication policy including authorship criteria, please refer to the Novartis publication policy training materials that were provided to you at the study Investigator meetings.

13.4 Quality control and quality assurance

Novartis maintains a robust Quality Management System that includes all activities involved in quality assurance and quality control, to ensure compliance with written Standard Operating Procedures as well as applicable global/local GCP regulations and ICH Guidelines.

[figure not shown]
Audits of Investigator sites, vendors, and Novartis systems are performed by auditors, independent from those involved in conducting, monitoring or performing quality control of the clinical study. The clinical audit process uses a knowledge/risk based approach.

Audits are conducted to assess GCP compliance with global and local regulatory requirements, protocols and internal SOPs, and are performed according to written Novartis processes.

14 Protocol adherence

This protocol defines the study objectives, the study procedures and the data to be collected on study participants. Additional assessments required to ensure safety of subjects should be administered as deemed necessary on a case by case basis. Under no circumstances including incidental collection is an Investigator allowed to collect additional data or conduct any additional procedures for any purpose involving any investigational drugs under the protocol, other than the purpose of the study. If despite this interdiction prohibition, data, information, observation would be incidentally collected, the Investigator shall immediately disclose it to Novartis and not use it for any purpose other than the study, except for the appropriate monitoring on study participants.

Investigators ascertain they will apply due diligence to avoid protocol deviations. If an Investigator feels a protocol deviation would improve the conduct of the study this must be considered a protocol amendment, and unless such an amendment is agreed upon by Novartis and approved by the IRB/IEC and health authorities, where required, it cannot be implemented.

16.1 Appendix 1: Clinically notable laboratory values and vital signs

The following criteria will be used to define expanded limits and notable abnormalities of key laboratory tests. Notable values for blood pressure and pulse are presented in [Table 8-5](#).

Liver function and related variables

Total bilirubin:	> 2 x upper limit of normal (ULN)
Alkaline phosphatase:	> 2.5 x ULN

Renal function and electrolyte variables

Creatinine (serum):	> 1.5 x ULN
Potassium:	> 6 mmol/L or < 3 mmol/L
Sodium:	> 160 mmol/L or < 115 mmol/L

Urinalysis variable

Protein urine dipstick:	2+ (100 mg/dL)
-------------------------	----------------

Hematology variables

Hemoglobin:	≥ 20 g/L decrease from Baseline
Platelet count:	< lower limit of normal (LLN)
White blood cell count:	< 0.8 x LLN
Neutrophils:	< 0.9 x LLN
Eosinophils:	> 1.1 x ULN
Lymphocytes:	> 1.1 x ULN

16.2 Appendix 2

16.2.1 Skin type classification scale

Fitzpatrick Classification Scale			
Skin Type	Skin Color	Characteristics	Score
I	White; very fair; red or blond hair; blue eyes; freckles	Always burns, never tans	(scores 0–6)
II	White; fair; red or blond hair; blue, hazel, or green eyes	Usually burns, tans with difficulty	(scores 7–13)
III	Cream white; fair with any eye or hair color; very common	Sometimes mild burn, gradually tans	(scores 14–20)
IV	Brown; typical Mediterranean caucasian skin	Rarely burns, tans with ease	(scores 21–27)
V	Dark Brown; mid-eastern skin types	very rarely burns, tans very easily	(scores 28–34)
VI	Black	Never burns, tans very easily	(scores 35–36)
